The failure to accurately differentiate between bipolar and unipolar symptoms represents a crisis. Current assessments often fail to identify the risk of developing manic symptoms in bipolar patients who seek treatment during a depressive episode. Further, standard pharmacotherapy for unipolar depression can trigger or exacerbate manic symptoms (Almeida & Phillips, 2012; Cusin et al., 2007). Given that manic episodes can result in devastating financial, legal, and professional consequences as well as heightened risk for self-destructive behavior, the need to understand the pathophysiological mechanisms that differentiate unipolar and bipolar depressive symptomatology is crucial (Almeida & Phillips, 2012; Cusin et al., 2007; Valenti et al., 2012).

The current proposal was developed to address these limitations by taking a transdiagnostic approach focused on the key domain of Reward Learning within the PVS matrix. As summarized in the RDoC workshop proceedings, Reward Learning cuts across several DSM

diagnoses, and is described as “*a process by which organisms acquire information about stimuli, actions, and contexts that predict positive outcomes*”. Reward and reinforcement learning has been strongly linked to a wide range of disorders, as well as individual symptoms involving anhedonia, substance use, impulsivity (e.g., Barch & Dowd, 2010; Mason et al., 2012; Robinson & Berridge, 2008).

II. SPECIFIC AIMS

a. Objectives and hypotheses

Specific Aim 1: To investigate reward learning across four units of analyses within the mood disorder spectrum. One hundred sixty (n=160) individuals seeking treatment for mood disorders at three mood disorder clinics will be enrolled, and screened with the PRT. Using normative control data from 821 control subjects, 50% (n=80) of this sample will be asked to return for subsequent study sessions. Importantly, subjects in this sub-sample will be selected so that each quintile of the normative distribution of reward learning is equally represented (n=16 per quintile). Symptom severity measures will also be acquired and used to ensure that at least 33% of the total sample exhibits some degree of manic/hypomanic symptoms or severe depression. This sub-sample will then be further tested across four units of analysis: molecules, circuits, physiology, and behavior. Data will also be collected on 32 healthy controls, who will serve as a reference point for all measures.

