Hypothesis 1: We will identify the units of analysis that show the strongest relative loading onto 3 reward-relevant symptom assessments in the areas of anhedonia, impulsivity, and mania across patients and controls.

Specific Aim 2: To investigate the predictive validity of reward learning units in a naturalistic follow-up study.

Hypothesis 2a: Relative weights for each unit of analysis for each symptom assessment area derived in Aim 1 will be used to predict the presence of anhedonic, manic and impulsive symptoms as assessed via phone interview at 3- and 6-month follow-up intervals. We predict that our units of analysis will have significant incremental predictive validity in predicting these domains while controlling for baseline severity.

Hypothesis 2b: Individuals who present at baseline with depressive symptoms but show an elevated response bias and enhanced PE signaling will show less symptom improvement following SSRI treatment in a naturalistic design (i.e., there is no treatment component to the study, but it is expected that many patients recruited through clinics will be receiving SSRI treatment).

III. SUBJECT SELECTION

a. Inclusion and exclusion criteria

General Exclusion Criteria

- 1) Suicidal ideation where outpatient treatment is determined unsafe by the study clinical interviewer. These patients will be immediately referred to appropriate clinical treatment;
- 2) Pregnant women or women of childbearing potential who 1) have not completed a negative urine pregnancy test prior to the MRI scan and/or 2) are seeking to become pregnant or believe that they may be pregnant

- 3) Serious/unstable medical illness (e.g., cardiovascular, renal, endocrine, neurologic disease);
- 4) Clinical or laboratory evidence of hypothyroidism;
- 5) History of seizure disorder, history or current diagnosis of dementia, score < 26 on the MMSE at screening;
- 6) History or current diagnosis of the following DSM-IV psychiatric illness: organic mental disorder, schizophrenia, schizoaffective disorder, delusional disorder, psychotic disorder NOS, patients with mood congruent or mood incongruent psychotic features
- 7) Lifetime history of stimulant dependence (e.g., cocaine, amphetamines)**;
- 8) Current use of Methylphenidate (Ritalin) and other ADHD medications with dopaminergic effects**;
- 9) Patients who have had electroconvulsive therapy (ECT) in the past 2 years;
- 10) Failure to meet standard MRI safety requirements;

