[** These exclusion criteria are included due to the proposed focus on reward learning, which relies on dopaminergic-rich brain circuitry and would thus be strongly affected by lifetime stimulant dependence and current treatment with methylphenidate or other ADHD medications.]

Inclusion Criteria: Mood Disorder Patients (n = 160)

- 1) Non-psychotic individuals seeking treatment at the Mass General Hospital (MGH) Depression Clinical and Research Program (DCRP), MGH Bipolar Clinical and Research Program (BCRP), and McLean Hospital Bipolar Disorder Program
- 2) Written informed consent;
- 3) Both genders and all ethnic origins, age between 18 and 65;
- 4) Right-handed (Chapman and Chapman, 1987);
- 5) Normal or corrected-to-normal vision and hearing
- 6) Absence of current illicit drug use (cocaine, amphetamines and cannabis) as assessed by urine drug test.
- 7) Stable medication over the past 8 weeks OR absence of any psychotropic medications for at least 2 weeks (for follow-up analyses testing effects in medication-free patients):
 - 6 weeks for fluoxetine,
 - 6 months for neuroleptics,
 - 2 weeks for benzodiazepines,
 - 2 weeks for any other antidepressants
 - 4 weeks for any mood-stabilizers

Inclusion Criteria: Healthy Controls (n = 32)

Absence of medical, neurological, and psychiatric illness (including alcohol and substance abuse), as assessed by subject history and a structured clinical interview (SCID-I/NP).

- 2) No family history of mood disorders;

- 3) Written informed consent;
- 4) Both genders and all ethnic origins, age between 18 and 50;
- 5) Right-handed (Chapman and Chapman, 1987).
- 6) Normal or corrected-to-normal vision and hearing
- 7) Absence of current illicit drug use (cocaine, amphetamines and cannabis) as assessed by urine drug test.
- 8) No psychotropic medication.

b. Source of subjects and recruitment methods

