Patient recruitment will be performed at the MGH DCRP and BCRP under the supervision of Drs. [name] and [name], respectively, and at the McLean Hospital Schizophrenia and Bipolar Disorder Program under the supervision of [name]. Healthy controls will be recruited by members of [name] laboratory, which is located in the Center for Depression, Anxiety and Stress Research at McLean Hospital. Prospective healthy control subjects will undergo a phone screen, which will include an overview of study details along with questions to assess inclusion/exclusion criteria. Eligible individuals will be invited to [name] lab to complete two testing sessions involving computer tasks (such as the PRT), clinical interviews, an EEG session and a neuroimaging session. Informed consent will be collected at these sessions. **Importantly, no subject will be asked to delay or stop treatment for the purpose of participating in the studies described in this proposal.**

IV. SUBJECT ENROLLMENT

a. Methods of enrollment

One hundred sixty (160) individuals between 18 and 65 years old who meet all inclusion and exclusion criteria and are currently experiencing depressive and/or manic or hypomanic symptoms will be recruited from the Depression Clinical and Research Program (DCRP; Director: [name]) and the Bipolar Clinical and Research Program (BCRP; Director: [name]) at Massachusetts General Hospital (MGH). Additional recruitment will occur from the Schizophrenia and Bipolar Disorder Program (SBDP; Clinical Director: [name]) and Center for Depression, Anxiety and Stress Research (CDASR; Director: [name]) at McLean Hospital. After providing written informed consent, these patients will first perform a computer task, the Probabilistic Reward Task (PRT), to determine their eligibility to continue in the study. Of the 160 patients screened, 80 will be brought back for further testing. In addition to this patient sample, 32 psychiatrically healthy individuals will be enrolled from the community.

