For patient participants (n=160), data from the PRT will be immediately classified relative to norm-referenced data from our normative database, using a gender-specific cutoff for each quintile to determine subject eligibility to continue in the study. From the initial sample of 160 participants who completed the screening session including the PRT, 50% (80) will be selected to continue for the behavioral and neuroimaging sessions. Importantly, subjects in this sub-sample will be selected so that each quintile of the normative distribution of reward learning is equally represented (n=16 per quintile). For comparison to the treatment-seeking individuals with mood disorders, 32 psychiatrically healthy and demographically matched individuals will be recruited and will also complete the PRT.

Participants will be observed with HIPAA-compliant teleconferencing software ‘blue jeans’ or ‘vidyo’ as they complete the PRT in order to verify compliance with task instructions while not impacting performance by directly observing from the same room. Video will not be recorded, only streamed.

Saliva Sample Collection and Analysis

During the Screening Visit, after participant eligibility is established, an additional saliva sample will be collected using Oragene DNA Collection Kit (DNA Genotek, Ottawa, Canada; <http://www.dnagenotek.com/>). The participant will be asked to spit into the collection tube to the fill line (2mL sample) and close with a stopper. The samples will be assayed for genetic information by the [name] Laboratory (Director: [name]) in the Psychiatric & Neurodevelopmental Genetics Unit at Massachusetts General Hospital, which provides core services for genetic assays.

Session 2 (Behavioral Session)

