Behavioral Data: For the PRT, the main dependent variable will be Reward Learning, as operationalized as the increase in response bias during the final block relative to the first block [= DResponse Bias = Response Bias(Block 3) - Response Bias(Block 1)]. This variable was selected because it has been repeatedly linked to current and future anhedonic symptoms (Pizzagalli et al., 2005, 2008b; Vrieze et al., 2013a).

b. Study endpoints

Not applicable

c. Statistical methods

Data analyses will proceed in two stages. First, descriptive statistics and graphs will be used to assess the presence of skewness and/or outliers in the four main variables of interest (*Aim 1*). Continuous/quantitative variables will be appropriately transformed. Similarly, covariates in regression analyses (*Aims 1 & 2*) will be summarized to determine whether a continuous versus categorical representation is the most appropriate. For these regressions, the analytic approach will address the type of outcome (e.g., continuous or discrete) and the functional relationship between covariates and outcome (e.g., linear versus non-linear). The second stage will involve the analyses of the central hypotheses in *Aims 1-2*:

Aim 1: For Hypothesis 1, we will first use multiple regression to examine the relationships between our behavioral and neuroimaging measures and the symptom domains of anhedonia, mania and impulsivity, which will be assessed using the symptom severity collected during session 2. Standard multiple regression techniques will be used to identify the optimal weights for each unit of analysis (MRS, fMRI striatal PE signals, ERP FRN, PRT response bias). Additionally, to take advantage of the correlations between the three symptom domains and to potentially improve predictive accuracy, a single multivariate analysis (canonical correlation analysis) will be used to assess a separate set of weights reflecting the contribution of each unit in relationship to all three symptom domains simultaneously. For ease of interpretation, the latter analysis will be based on the first pair of canonical variables. Models will be fit using SAS PROC CANCORR.

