For group comparisons, multiple past studies using the PRT have found that unmedicated MDD subjects exhibited reduced reward learning compared to controls (Cohen's $d: -0.70$; Pizzagalli et al 2008c; Cohen's $d: -0.61$; Vrieze et al 2013a). In contrast, euthymic individuals with bipolar disorder had significantly higher reward learning relative to controls (Cohen's $d: 0.72$) (Pizzagalli et al 2008b). For the reinforcement learning task proposed for our fMRI study (Pessiglione et al 2006), we found that, relative to healthy controls, MDD subjects had significantly lower accuracy during reward learning (Cohen's $d: -1.54$). These effect sizes translate to power >0.98 for detecting group differences with the proposed sample size. For dimensional approaches, past studies have shown a strong large effect for the relationship between reward learning and anhedonic symptoms in BPD patients ($r = -0.59$). Moreover, among healthy subjects, reward learning predicted anhedonic symptoms 30-40 days later ($r = -0.41$, $p < 0.05$). In light of these effect sizes, a total of 80 individuals with mood disorders leads to a power of >0.97 of (1) detecting relationships between units of analysis and reward-related symptoms (e.g., anhedonia, mania), and (2) predicting clinical outcome in the naturalistic follow-

up study. Finally, in an fMRI study probing reward processing, unmedicated MDD subjects showed weaker activation than controls to gains in the caudate ($d = -0.98$) and left Nac ($d = -0.73$) and left putamen ($d = -0.78$) during reward anticipation (Pizzagalli et al 2009), yielding a mean effect size of -0.87. In light of an average ES of 0.83 in the fMRI study, a total of 80 individuals with mood disorders and 32 healthy controls leads to a power >0.97 of detecting group differences.

VII. RISKS AND DISCOMFORTS

The risks associated with participation in this study are minimal, and every possible precaution is being taken to further reduce potential risks, as described below:

Behavioral component. We foresee no risks from the behavioral tasks required for the proposed research.

Genetic component.

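### Controls stop at age 50 and patients at 65, so the matched controls cannot cover patients aged 51-65

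*Combined protocol and SAP*

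**What the plan says.** Two eligibility lists in III.a set different upper ages. For patients: "Both genders and all ethnic origins, age between 18 and 65". For healthy controls: "Both genders and all ethnic origins, age between 18 and 50". Section IV.a repeats the patient range: "One hundred sixty (160) individuals between 18 and 65 years old". No reason is given for the difference.

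The controls have three roles:

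- **Matched group.** V.a (PRT Data Collection and Scoring): "32 psychiatrically healthy and demographically matched individuals will be recruited". The matching variables, method and tolerance are not stated.
- **Reference.** II.a, Specific Aim 1: "Data will also be collected on 32 healthy controls, who will serve as a reference point for all measures".
- **Part of the Hypothesis 1 sample.** II.a relates the units of analysis to "anhedonia, impulsivity, and mania across patients and controls".

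VI.d also bases a power statement on the two groups: "a total of 80 individuals with mood disorders and 32 healthy controls leads to a power >0.97 of detecting group differences".

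VI.c foresees covariates in the Aim 1 and Aim 2 regressions, which "will be summarized to determine whether a continuous versus categorical representation is the most appropriate", but lists none. Age is not mentioned there. The PRT quintile cutoffs are specific to gender only.

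**The concern.** A control group capped at 50 cannot be matched across the age range of a patient group that runs to 65. If prediction-error BOLD signal, Gln/Glu, the ERP measure or reward learning varies with age, part of a patient-control difference would be an age difference.

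If the Hypothesis 1 regressions pool the two groups, part of the fitted weights could also reflect age. Hypothesis 2a then reuses those weights, so any distortion would carry into Aim 2.

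The 821-person database supplies norms for the PRT only, and its age range is not given. For MRS, fMRI and ERP the 32 controls are the only healthy reference, and above 50 there is none.

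**Working it through.** **Plan's own figure.** VI.d: 80 patients, 32 controls, average d = 0.83; VI.d sets two-sided alpha at 0.05. Noncentrality = d × √(n₁n₂/(n₁+n₂)) = 0.83 × √(80×32/112) = 0.83 × 4.781 = 3.97, with 110 degrees of freedom. Two-sample t-test power is 0.976, so the stated >0.97 reproduces.

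**Uncovered range.** In completed years, patients span 18-65 (48 years of age) and controls 18-50 (33). The uncovered part is 51-65: 15 of 48, or 31%. This follows from the documents alone.

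**Possible imbalance.** All inputs here are assumptions. Patient ages are taken as normal with SD 13, truncated to 18-65 and centred on 35 or 40, or as uniform on 18-65. Controls follow the same distribution cut at 50, that is, not otherwise selected for age. Spurious d = r × (mean gap) / (patient age SD), with age-outcome correlation r of 0.2 to 0.4.

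| Patient ages | Aged 51-65 | Of 80 | Mean age, patients v controls | Gap (years) | Age SD | Spurious d |
|---|---|---|---|---|---|---|
| Centre 35 | 11% | 9 | 37.1 v 34.7 | 2.4 | 10.6 | 0.05-0.09 |
| Centre 40 | 19% | 15 | 40.6 v 36.8 | 3.7 | 10.95 | 0.07-0.14 |
| Uniform | 31% | 25 | 41.5 v 34.0 | 7.5 | 13.85 | 0.11-0.22 |

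Example, uniform: 0.2 × 7.5/13.85 = 0.11 and 0.4 × 7.5/13.85 = 0.22. With no true difference, an 80 v 32 test would reject about 6% of the time at d = 0.05 and 18% at d = 0.22, against a nominal 5%.

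**Pooled Hypothesis 1 weights, rough ceiling.** The correlation of age with group membership (80 v 32) is 0.11, 0.16 and 0.26 in the three scenarios. Multiply by r = 0.2-0.4 and suppose that symptoms coincide perfectly with group. The induced measure-symptom correlation is then 0.02-0.04, 0.03-0.06 and 0.05-0.10. Real overlap in symptoms would lower it. VI.d plans on correlations of 0.41 and 0.59 in absolute value.

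**Matching on mean age alone.** In the uniform case controls would need a mean of 41.5 from a range ending at 50. Exponentially tilting a uniform 18-50 distribution to that mean puts 64% of controls at 41-50, against 10/48 = 21% of patients, with age SD 7.7 v 13.9. The means agree but the distributions do not, so a non-linear age effect would remain.

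**Restricting the contrast to age 50 or younger** (32 controls, two-sided 0.05, before the planned 15% loss):

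| Patients kept | Power, d = 0.83 | Power, d = 0.61 |
|---|---|---|
| 80 (no restriction) | 0.976 | 0.824 |
| 71 | 0.971 | 0.810 |
| 65 | 0.967 | 0.798 |
| 55 | 0.958 | 0.774 |

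**The case against.** The strongest reply is that little depends on this.

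- VI.c specifies no patient-control test; group contrasts appear only in the power section. This is correct.
- Pooling for Hypothesis 1 rests on its wording in II.a. VI.c does not state the analysis set, and the dimensional power statement cites only the 80 patients. So the point about pooled weights holds only if controls are pooled.
- Age confounding within patients aged 18-65 would exist even with perfectly matched controls. True, but the cap adds a separate source.
- The spurious effects are small beside the planned ones, and the scenarios assume controls are not selected for age although V.a promises matching. Both are fair. Matching on mean age is feasible under the cap, at the cost in distribution shown above.
- Age could enter under the unnamed covariates. It could, but above 50 the model would extrapolate the age relation for controls.
- Widening the range would yield only a few older controls. A thin reference above 50 is still better than none.

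These replies limit the size of the problem. They do not reconcile the two age limits with the matching statement and the reference role.

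**Conclusion.** The concern holds. The missing control coverage at 51-65 is certain from the eligibility lists, and nothing elsewhere in the document resolves it. Any resulting bias is uncertain and probably small: spurious d of 0.05 to 0.22 under the assumed age distributions and correlations, against planned effects of 0.61 to 1.54 in absolute value. It matters most if many patients over 50 are retained and a measure is strongly related to age. Quintile selection and patient-only analyses are untouched. This should be changed because the correction is cheap, not because it threatens the main aims.

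**What to change.** Set the control age range in III.a to 18-65. In V.a, name age and sex as the matching variables and frequency-match the 32 controls to the 80 retained patients.

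This is a one-line eligibility change plus a sentence on matching, at the same n = 32. Under the scenarios above, about 4 (32 × 0.112 = 3.6) to 10 (32 × 0.3125) controls would be aged 51-65, and these may be slower to recruit. The retained patients' ages emerge only as screening proceeds, so the control age targets need updating along the way.

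If the cap of 50 stays, make the contrast in participants aged 50 or younger the matched comparison. Name age as a covariate in any pooled Hypothesis 1 model, and state that adjustment above 50 is extrapolation for controls. This is the weaker option: it removes 9 to 25 patients from the group contrast, and power becomes 0.96-0.97 at d = 0.83 and 0.77-0.81 at d = 0.61, before attrition.

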Aim 2: For Hypothesis 2a, symptom inventories collected during follow-up interviews will be used to investigate incremental predictive validity of each unit of analysis in predicting subsequent symptoms while controlling for baseline severity. For these models, our behavioral and neuroimaging measures will be modeled using the relative weighting derived from the analyses described in aim 1. For quantitative measures (e.g., depressive and anhedonic symptoms), linear mixed effects models will be used. These models incorporate random subject effects to account for correlation among the repeated outcome measures (months 0, 3, 6); models will be fit using SAS PROC MIXED. Hypotheses concerning frequency measures (e.g., frequency of impulsive/risky behaviors) will be tested in a similar way. Models will be fit using SAS PROC GENMOD. Statistical tests and confidence intervals will be based on the “sandwich” estimator of standard errors to ensure that correlation among repeated assessments and overdispersion is accounted for.

d. Power analysis

Sample size and power calculations

Sample size determination was calculated based on observed effect sizes derived from prior studies that in our lab. Effect sizes were calculated using $\alpha = 0.05$ (two-tailed) for (1) detecting relationships between reward learning variables across different unit of analyses and reward-related symptoms (e.g., anhedonia, mania); and (2) to predict symptom severity measures in a naturalistic follow-up study. Based on these estimates and allowing for 15% patient attrition or data loss, the sample will be: 80 treatment-seeking individuals with mood disorders recruited from three clinics as well as 32 psychiatrically healthy controls.

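### The power above 0.98 claimed for PRT group differences takes no account of selecting the 80 patients on the PRT reward-learning score itself

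*Combined protocol and SAP*

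**What the plan says.** Section V.a (Session 1, PRT Data Collection and Scoring) screens 160 patients with the PRT, classifies each against gender-specific quintile cutoffs from the normative database, and continues with 80: "subjects in this sub-sample will be selected so that each quintile of the normative distribution of reward learning is equally represented (n=16 per quintile"). Specific Aim 1 (II.a) states the same rule and gives the norm as 821 healthy controls. Section VI.a makes reward learning (response bias in block 3 minus block 1) the main PRT variable, so the sample is selected on the construct that is later analysed.

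The controls are not selected on the PRT: "For comparison to the treatment-seeking individuals with mood disorders, 32 psychiatrically healthy and demographically matched individuals will be recruited and will also complete the PRT".

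Section VI.d sets the sample as "80 treatment-seeking individuals with mood disorders recruited from three clinics as well as 32 psychiatrically healthy controls", with two-sided alpha 0.05. Under group comparisons it cites PRT effects of d = -0.70 and -0.61 (unipolar v controls) and +0.72 (euthymic bipolar v controls), plus d = -1.54 for accuracy on the fMRI learning task, and concludes: "These effect sizes translate to power >0.98 for detecting group differences with the proposed sample size". Selection is not mentioned. Section VI.c contains regressions, canonical correlation and repeated-measures models, but no patient-control model.

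**The concern.** Placing one fifth of the patients in each healthy quintile gives them nearly the healthy distribution of the screening score, whatever the distribution among all screened patients. VI.d does not describe the groups behind its PRT effects as selected on that score, so the effects cannot be carried unchanged to the selected 80.

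At stake are part of the sample-size justification and how a null result is read. A pooled 80 v 32 comparison of session 1 scores would show almost nothing even if patients differed markedly from controls, and could be reported as intact reward learning in mood disorders. Unselected session 1 scores exist for all 160 patients, but no comparison is assigned to them.

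**Working it through.** **Inputs.** From VI.d: two-sided alpha 0.05, n = 80 and 32, d = -0.70, -0.61, +0.72 and -1.54. From V.a: 16 patients per healthy quintile. Assumed: healthy scores N(0,1), patient scores N(μ,1) with μ equal to the cited d, and test-retest correlations of 0.3 to 0.7, which the documents do not give.

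**1. The plan's figure.** Power is from the noncentral t with noncentrality d·√(n₁n₂/(n₁+n₂)); at 80 v 32 the multiplier is √(2560/112) = 4.78.

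| d | Power, 80 v 32, no selection |
|---|---|
| 0.61 | 0.82 |
| 0.70 | 0.91 |
| 0.72 | 0.93 |
| mean of all four, (0.70+0.61+0.72+1.54)/4 = 0.8925 | 0.99 |

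Power of 0.98 needs d of about 0.85. The stated figure is reached only by averaging in the fMRI-task effect; the plan does not say whether it did so. With the 15% loss taken from the 80 (68 v 32), the PRT effects give 0.80 to 0.91.

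**2. Pooled session 1 score after selection.** The healthy cutpoints are ±0.842 and ±0.253. In a quintile with limits a and b, the patient mean is μ + [φ(a-μ) - φ(b-μ)]/[Φ(b-μ) - Φ(a-μ)]. For μ = -0.70 the five means are -1.590, -0.552, -0.015, 0.512 and 1.274 (healthy: -1.400, -0.532, 0, 0.532, 1.400). Equal weighting gives -0.371/5 = -0.074.

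| Effect before selection | Pooled difference after | Power, 80 v 32 |
|---|---|---|
| -0.70 | -0.074 | 0.06 |
| -0.61 | -0.064 | 0.06 |
| +0.72 | +0.076 | 0.06 to 0.07 |

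With the quotas filled, the simulated rejection rate for an all-unipolar cohort (d = -0.655, the mean of -0.70 and -0.61) is lower still, 0.027, because the quota also fixes the patient mean.

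**3. Mixed cohort, unipolar -0.655 and bipolar +0.72.** With unipolar share w and quintile shares pᵤ and p_b, the expected unipolar count among the 16 in a quintile is 16·w·pᵤ/[w·pᵤ + (1-w)·p_b]. At w = 0.5 the counts are about 14.1, 10.9, 8.2, 5.4 and 2.1, in all about 41.

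| Unipolar share | Pooled before | Pooled after | Unipolar v 32 after | Bipolar v 32 after |
|---|---|---|---|---|
| 33% | +0.27 | +0.02 | -0.70 (power 0.77) | +0.46 (0.51) |
| 50% | +0.03 | +0.004 | -0.56 (0.65) | +0.59 (0.68) |
| 67% | -0.20 | -0.01 | -0.43 (0.48) | +0.73 (0.80) |

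At 50:50 both contrasts shrink. In unequal mixes the majority diagnosis shrinks and the minority stays near its original size, but with only about 30 patients.

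**4. Session 2 score.** The expected difference is μ + r·(selected mean - μ). For μ = -0.70: -0.51, -0.39 and -0.26 at r = 0.3, 0.5 and 0.7, with power 0.68, 0.45 and 0.24.

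**5. All 160 screened, by diagnosis.** With 80 of each diagnosis v 32 controls, power is 0.87 for -0.655 and 0.93 for +0.72.

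**The case against.** The strongest reply is that no 80 v 32 PRT test is specified. The hypotheses in II.a contain no patient-control contrast, VI.c has no such model, and the controls are introduced as a reference point. The sentence recruiting them does not say whether they are compared with the 80 or the 160, or on which PRT session. This stands, and it limits the point to the power statement and to any comparison made informally. It does not rescue VI.d, which ties its figure to the proposed sample.

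Second, a cohort shifted wholly one way is not what the clinics will supply. In a 50:50 mix the pooled difference is already about 0.03 before selection, so opposite signs, not the quota, remove it. Nor would a one-way cohort fill the quotas easily: at d = -0.655 only 10.8 of 160 are expected in the top quintile, all five quotas fill in about 5% of simulations, and taking up to 16 per quintile leaves about -0.17 with a rejection rate of 0.11. Both points stand; pooled power stays far below 0.98.

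Third, quintile sampling is deliberate, to cover the full range of reward learning. That is sound for the dimensional aims and is not disputed.

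Fourth, effects on the other units may be small. With an assumed PRT-fMRI correlation of 0.3 and a one-way shift of -0.70, an fMRI effect of -0.83 becomes -0.83 + 0.3 × (0.70 - 0.074) = -0.64, power about 0.86. This supports a sensitivity analysis, not a claim that those contrasts fail.

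**Conclusion.** The claim of power above 0.98 does not hold for PRT group differences in the selected 80. The three PRT effects miss it before selection (0.82 to 0.93). After selection, the pooled session 1 contrast has power of about 0.06 in a one-direction cohort with filled quotas, and is below 0.02 SD in 33% to 67% unipolar mixes. Contrasts by diagnosis keep power of about 0.5 to 0.8.

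A reader might go further and infer that the PRT comparison is null by construction, or that the cited effects cannot survive in the 80. The documents do not support that. Near-nullity by construction applies to the pooled session 1 score only. The cited effects are diagnosis-specific and persist in a mixed cohort, the session 2 score recovers part of a one-way difference, and no stated hypothesis or VI.c analysis is invalidated.

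The sizes rest on normal scores with equal SDs, assumed retest correlations, and the bipolar sign in VI.d. That sign needs checking: the reference-list title of the euthymic bipolar study reports decreased reward learning, while VI.d reports higher. If both diagnoses shift downward, the one-direction figures are the relevant ones.

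**What to change.** - In VI.d, withdraw or restate the power above 0.98 for PRT group differences, and say that the cited PRT effects do not apply unchanged to the quintile-selected 80. Reconcile the bipolar sign first.
- State that any patient-control PRT comparison uses the session 1 PRT of all 160 screened patients against the 32 controls, separately for unipolar and bipolar patients, and that a null pooled 80 v 32 PRT result is not read as intact reward learning.
- For group contrasts on fMRI, ERP and MRS in the 80, add a sensitivity analysis weighted by the inverse of each patient's actual selection probability, with the unweighted result alongside. Take the probabilities from achieved counts by gender-specific quintile and any symptom-severity quota (Aim 1 requires at least 33% with manic/hypomanic symptoms or severe depression). Assuming a fixed 20% per quintile would ignore these and any unfilled quota.
- Keep the quintile-balanced 80 for the dimensional aims.

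The cost is protocol wording and one added analysis, with no new data. Weighting loses some precision, and the stated group power becomes less favourable.
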